APPENDIX I: RESULTS OF CENICRIVIROC MESYLATE (CVC) STUDIES

Appendix I Table 1

Study Number/Phase	Study Title	Participant Description	Dose & Administration	CVC Formulation	Endpoints
Allergan Study 652-1-104 Phase 1	A phase 1 multiple-dose, cross-over study to assess the potential interaction between TBR-652 and RTV in healthy volunteers	20 healthy adults	50 mg CVC po × 10 days, then 50 mg CVC + 100 mg RTV po × 10 days (CVC administered as 2×25 mg tablets after a standardized meal) [Standardized meal contained approximately 500-700 kcal and <15-20 g fat]	DP3_25 formulation, manufactured by Emerson Resources	1. Plasma PK of CVC with/without RTV 2. Safety, tolerability
Noteworthy Findings:					
RTV significantly increased exposure to CVC (based on ratios of LS geometric means: 2.39-fold increase in Cmax and a 3.55-fold increase in AUC0-24) and reduced exposure to CVC metabolites. There were no clinically important safety findings.					
Allergan Study 652-1-105 Phase 1	A phase 1, open-label, single-dose, randomized, cross-over study to assess the potential interaction between TDF and TBR-652 in healthy volunteers	21 healthy adults	150 mg CVC po, 300 mg TDF, 150 mg CVC po + 300 mg TDF (CVC administered as 6×25 mg tablets after a standardized breakfast) [Standardized breakfast contained approximately 500-700 kcal and <15-20 g fat] 14-day washout between regimens	DP3_25 formulation, manufactured by Emerson Resources	1. Plasma PK of CVC with/without TDF 2. Plasma PK of TDF with/without CVC 3. Safety, tolerability
Noteworthy Findings:					
TDF had no effect on CVC exposure. Co-administration of CVC and TDF did not affect the AUC0-t and AUC0-∞ of TDF, based on the protocol-defined equivalence range of 0.70-1.43. However, co-administration with CVC increased the AUC and Cmax of TDF by approximately 28%-36%, with the 90% CI for the Cmax of TDF falling outside the 0.80-1.25 “no effect” range. There were no clinically important safety findings.					

Study Number/Phase	Study Title	Participant Description	Dose & Administration	CVC Formulation	Endpoints

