2.3.3 Exploratory Objectives

- 1) To measure the effects of CVC on adipocytokines (adiponectin) and on noninvasive assessments of liver fibrosis, including AST to Platelet Ratio Index (APRI) and Fibrosis-4 (FIB-4).
- 2) To assess changes in FDG uptake in visceral fat and to quantify changes in visceral adipose tissue area and volume, subcutaneous adipose tissue area and volume, fat density, and liver to spleen attenuation ratio (as a noninvasive measure of hepatosteatosis) by noncontrast CT after treatment with CVC compared to placebo.
- 3) [PK/PD] To determine the association between CVC trough exposure and the primary treatment outcome (i.e., reduced arterial inflammation).
- 4) To evaluate the effects of CVC on markers of monocyte and T cell homing and activation as well as on myeloid cells.
- 5) To assess changes in occupancy of the CCR5 and CCR2 receptors on T cells and monocytes after treatment with CVC compared to placebo.
- 6) [PK/PD] To evaluate potential drug interactions by a) investigating the impact of INSTI- and NNRTI-based ART on CVC trough estimates and to compare these estimates across regimens and b) investigating the impact of CVC treatment versus no treatment on the trough exposure of ART.

Note: The Study Pharmacologist is evaluating currently available data on the effects of CVC on ART exposures to determine ARTs would be of interest for part b) of this objective.

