4.2 Analysis Approaches

- Descriptive summaries in Section 5 will be presented for both the Safety set and Efficacy set, unless otherwise specified.
- Summary statistics for discrete and continuous outcomes will be detailed under each report-content in Sections 5 - 9.
- All statistical tests will be two-sided with a nominal alpha level of 0.05.
 - No adjustment for multiple testing will be performed.
- Stratification will be taken into account in efficacy outcome analyses unless stated otherwise.
- No statistical comparisons across groups for baseline characteristics are planned.
- Missing data for TBR analyses will be handled using multiple imputation; sensitivity analyses will be complete case where missing data are ignored.
- Missing data for biomarker analyses will be ignored (i.e., all analyses will be complete case).

Report Contents

5 Participant Characteristics and Disposition

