8.1.1 Distribution Plot of Biomarkers by Visit Week

Analysis set(s): Efficacy set

Stratification: Overall, by statin-use

Grouped by: Baseline, Week 24, Change

- Figure: Jitter and boxplot of biomarkers at baseline and week 24 by treatment arms (with a 3rd group of boxplots showing the within-participant change)

9 Pharmacokinetic (PK) / Pharmacodynamic (PD) Outcomes

Analyses in this section are subject to change based on pending review of current literature of CVC and ART drug-drug interactions. Based on review of participant regimens, only bictegravir (BIC), dolutegravir (DTG), rilpivirine (RPV), tenofovir alafenamide (TAF), emtricitabine (FTC), and lamivudine (3TC) have exposure by at least 10 participants.

All PK outcomes are limited to participants in the CVC arm.

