9.1.2 Change in ART Trough Estimates

Analysis set(s): Complete case set
Grouped by: Specific ART Bictegravir, Dolutegravir, Rilpivirine
Stratification: None
Analysis method: paired t-test of pre-study treatment and participant-level average post-study treatment ART trough estimates with null hypothesis of no difference between pre- and post- study measures.

Table	Columns for each group: Pre, Post, Change	
Characteristic	Pre-, Post- Treatment Statistic(s)	Change Statistic
Average <DRUG> trough concentration	Mean (st.dev.), Median (Q1, Q3), and P10, P90	Mean, 95% confidence interval, p-value

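### SAP 9.1.2 tests ART troughs for any difference, with no log scale and no reference range, so a non-significant result cannot support a statement of no interaction

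*SAP*

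**What the plan says.** One part of an exploratory objective in SAP 2.3.3 is "investigating the impact of CVC treatment versus no treatment on the trough exposure of ART". SAP 9.1.2 carries it out as a "paired t-test of pre-study treatment and participant-level average post-study treatment ART trough estimates with null hypothesis of no difference", grouped by "Specific ART Bictegravir, Dolutegravir, Rilpivirine". The change column of its table is "Mean, 95% confidence interval, p-value". SAP 4.2 adds "All statistical tests will be two-sided with a nominal alpha level of 0.05", with no adjustment for multiple testing.

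The introduction to SAP Section 9 states "All PK outcomes are limited to participants in the CVC arm". It lists six antiretrovirals, including these three, that "have exposure by at least 10 participants". It gives no count for any one drug, and marks the section's analyses as open to change after a literature review.

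SAP 9.1.2 mentions neither a transformation nor a range for reading the change. SAP 7.2 and Section 8, by contrast, address the log scale explicitly for TBR and soluble biomarkers. Protocol 11.3.2 plans mixed models on log-transformed concentrations for the PK analyses. Appendix I of the protocol reports Study 652-1-105 "based on the protocol-defined equivalence range of 0.70-1.43", and uses 0.80-1.25 as a no-effect range in Studies 652-1-105, 652-1-109 and 652-1-113.

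**The concern.** An interaction analysis has to separate three findings: exposure has shifted by an amount that matters, exposure is shown to be close to unchanged, or the data cannot tell. A test against exactly zero change addresses only whether there is any shift. A small group with variable troughs can give a large p-value while a 20% or 30% fall remains plausible. A larger group can give a small p-value for a shift that lies wholly inside the range Appendix I calls no effect.

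The scale adds to this. Read literally, the planned summary is a mean difference in concentration units. Such a difference and its CI cannot be set against ratio limits, or compared directly with the earlier CVC interaction studies. At stake is the wording of the interaction result for three drugs on which participants' viral suppression may depend.

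**Working it through.** The documents give no sample size, SD, margin or power for this comparison, so there is no planned figure to reproduce.

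**Inputs**
- Test: paired t, two-sided 5% (SAP 9.1.2 and 4.2).
- n: 10 is the floor in SAP Section 9; 20 and 30 are illustrative. At 2:1, about 110 × 2/3 = 73 participants are on CVC, divided among regimens.
- True ratio: 0.80 and 0.70, the lower limits of the Appendix I ranges. ln 0.80 = -0.223 and ln 0.70 = -0.357.
- SD of the paired log difference: **assumed 0.3 to 0.6**. The only anchor in the documents is CVC Cmin in Study 652-1-109: ratio 0.85, 90% CI 0.71-1.01, n = 20. The half-width is (ln 1.01 - ln 0.71)/2 = 0.176, so SD = 0.176 × √20 / 1.729 = 0.456. Splitting this equally over two single troughs gives 0.456/√2 = 0.322 each. One pre-treatment trough against the mean of four on-treatment troughs then gives 0.322 × √1.25 = 0.36. Both values fall inside the assumed range, but they describe CVC in healthy volunteers, not ART troughs in this trial.

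**Step 1: miss rate of the planned test (on the log scale)**
Noncentrality δ = |ln ratio| × √n / SD. Miss rate = P(|T| ≤ t(0.975, n-1)) for T noncentral t with n-1 df. Example: n = 10, SD 0.3, ratio 0.80 gives δ = 0.223 × 3.162 / 0.3 = 2.35, critical value 2.262, miss rate 44%.

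| n | 20% fall, SD 0.3 to 0.6 | 30% fall, SD 0.3 to 0.6 |
|---|---|---|
| 10 | 44% to 82% | 8% to 61% |
| 20 | 12% to 65% | 0% to 29% |
| 30 | 2% to 50% | 0% to 12% |

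At n = 10 and SD 0.456 the test misses 72% of 20% falls and 40% of 30% falls. At SD 0.36 the figures are 58% and 20%. For a 20% fall at n = 10, the miss rate passes one half once the SD exceeds about 0.32.

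**Step 2: the same data as a ratio with a 90% CI**
The CI is the estimate divided and multiplied by exp(t(0.95, n-1) × SD / √n).
- n = 10, SD 0.5: exp(1.833 × 0.5 / 3.162) = 1.34. An observed ratio of 1.00 gives p = 1 and a CI of 0.75-1.34. That is inside 0.70-1.43 but not inside 0.80-1.25.
- n = 30, SD 0.3: exp(1.699 × 0.3 / 5.477) = 1.10. An observed ratio of 0.89 gives t = 0.1165/0.0548 = 2.13, above the critical value 2.045, so p < 0.05. The CI is 0.81-0.98, inside the no-effect range.

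The p-value therefore points the wrong way in both cases relative to the narrower range.

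**The case against.** Several points on the other side are sound.

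- A reader might infer that the SAP will treat p > 0.05 as proof of no interaction. No section says so. SAP 9.1.2 also reports a 95% CI and full pre and post summaries. On the log scale at n = 10 and SD 0.36, that CI around a ratio of 1 would be about 0.77-1.29, so imprecision would be visible.
- A reader might infer that the test misses relevant changes most of the time. That does not follow for shifts of 20-30% in general. It fails for a 30% fall except near n = 10 with a high SD, and at n = 30 no assumed SD takes the miss rate above about half. The documents also set no relevant change and no SD.
- Ten is a floor across six drugs, so some groups are probably larger. Whether it counts both arms is not stated; if it does, about 10 × 2/3 ≈ 7 could be on CVC. The complete-case set, which requires paired scans, could reduce a group further.
- The log scale may be intended, since protocol 11.3.2 specifies it and the SAP leaves coding detail to the implementation plan.
- The objective is exploratory and the section provisional. Viral control is followed directly by HIV-1 RNA, and Appendix I already reports no effect of CVC on dolutegravir exposure.

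These points limit how much the gap matters. They do not fill it: a CI helps only if its scale and the range for reading it are stated, and SAP 9.1.2 states neither.

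**Conclusion.** The concern holds as a gap in specification, at low severity. SAP 9.1.2 gives a test of no difference without a log scale or reference range, while the protocol supplies the first in 11.3.2 and the earlier studies' ranges in Appendix I. That a non-significant p-value cannot support no interaction needs no assumption about SD. The size of the risk does: for a 20% fall the miss rate is 44-82% at n = 10 and 2-50% at n = 30; for a 30% fall it is 8-61% and 0-12%. All of these rest on an assumed paired log SD of 0.3-0.6 and on group sizes the documents do not report. The documents do not support saying that the SAP plans to misread its p-value, or that the test usually misses shifts of 20-30%.

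**What to change.** In SAP 9.1.2:
- Analyse log-transformed troughs, as protocol 11.3.2 specifies, and report for each drug the number of participants and the geometric mean ratio (on CVC / pre-CVC) with its 90% CI.
- State beforehand how the CI will be read: no effect if it lies within 0.80-1.25, equivalent if within 0.70-1.43, otherwise inconclusive. Name both ranges, because in Study 652-1-105 tenofovir AUC met the wider range while the Cmax CI fell outside the narrower one.
- State that p > 0.05 will not be interpreted as absence of interaction.

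The change is to wording only, uses the same samples, and fits a section still open to revision. The cost is more inconclusive results in small groups. With a true ratio of 1 and SD 0.456, the chance that the CI falls within 0.80-1.25 is about 6% at n = 10 and 67% at n = 30; for 0.70-1.43 it is about 49% and 99%. About 38 participants would be needed for 80% on the narrower range, or about 24 if the SD is 0.36. The fix leaves the pre/post contrast without a placebo control; the protocol's CVC-versus-placebo comparison of ART troughs is a separate matter to reconcile.

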9.1.3 Correlation between CVC Trough Exposure versus Index Vessel MDS TBR

Analysis set(s): Complete case set
Stratification: Overall, by statin-use
Analysis method: Spearman's rank-based correlation

- Figure: Scatterplot of Index Vessel MDS TBR vs CVC trough exposure
 - CVC exposure is based on composite time-adjusted CVC exposure estimate over the 24-week study period obtained from mixed-effect modelling based on measured concentrations at weeks 4, 8, 12, and 24 (see Protocol Section 11.3.2).
